13.2 Methods and Timing for Assessing, Recording, and Analyzing Safety Parameters

The risk profile for this study is low as it is a minimal risk, nonpharmacologic intervention. As such, assessing and recording of the parameters will be done by the PI with the end goal of informing the DSMC of any deviations. Since the PI and team of consultants will be intimately involved in all aspects of the trial, all subject data will be regularly reviewed by them and all staff will report to them on an ongoing basis, assuring that all issues are recorded on a timely basis and any AEs or SAEs are reported to the DSMC within 24-48 hours. The DSMC will be responsible for analyzing the associated data and determining if there are any study-related issues that need to be intervened upon.

Adverse Event (AE): Any untoward or unfavorable medical occurrence in a clinical research study participant, including any abnormal sign (e.g. abnormal physical exam or laboratory finding), symptom, or disease, temporally associated with the participants' involvement in the research, whether or not considered related to participation in the research.

Serious Adverse Event (SAE): Any adverse event that:

- Results in death
- Is life threatening, or places the participant at immediate risk of death from the event as it occurred
- Requires or prolongs hospitalization

- Causes persistent or significant disability or incapacity
- Results in congenital anomalies or birth defects

Safety reports will be sent to the DSMC quarterly and will include a detailed analysis of study progress, AEs, and SAEs.

13.3 Reporting Procedures

AEs and SAEs will be reported to the DSMC and the IRB by the PI within 48 hours of occurrence. Any deaths to study participants, from whatever cause, will be reported within 24 hours. The DSMC and IRB will then make the determination of whether they should be reported to the NIA. The severity of AEs and SAEs will be determined by the PI and Experimental Team Leader in consultation with the DSMC. The events will be recorded on the "Adverse Events Reporting Form" which includes the instructions for both where the form should be submitted and filed, as well as the reporting timeline required.

How AEs will be classified:

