All required data collection for the project will be described below with timelines, data sharing procedures, and contact information in case there are issues. For any data collection challenges, please contact Project Coordinator [name] – [contact] or [contact]. For clinical guidance, adverse reactions, or concerns about subject safety, reach out to Principal Investigator, [name]. For non-emergencies, email – [contact] -or- [contact]. For urgent matters, [name] may be reached at [contact].

All SHARE Program Counseling Data Collection Tools for Treatment Group Cases are listed below:

Post-Session Case Notes:

Electronic Case Files: Throughout your sessions, you are expected to take detailed notes in the electronic case file provided to you in your Microsoft Teams channel for each assigned case. You will upload the completed version into the Teams folder for each session within **48 hours** of completion. The electronic case file includes each of the following sections, per session:

- **Session Preparation:** A list of what tools you will need to have reviewed and/or ready prior to that session.
- **Changes Since Last Session:** Here you will report any major changes that either care partner has experienced since the last time you spoke with/met them. This is an important reporting requirement to our funder. If anything, major has occurred, please fill out an **Adverse Event Form** as soon as possible and send it as an encrypted file to [contact] within 24 hours -or- upload it to your Teams Channel.
- **Session Information:** Basic information about the session [date, time of session, session duration, PWD location, CG location).
- **Session Counselor Evaluation:** Each treatment session will include an evaluation of session components from your perspective.
- **Readiness Ratings:** You will rate each care partner's level of readiness at the end of each session and note any important contents to support your rating in the box provided.
- **Session Notes:** Complete notes on your session at the of the case file for that session.

Procedures:

- **Electronic Case File:** Save the document after each completed session and name the most recent case file into the Completed Data Folder for your case using the following convention:
 - #####_Session1_Case File Complete
 - #####_Session2_Case File Complete
 - #####_Session3_Case File Complete
 - #####_Session4_Case File Complete
 - #####_FamilySession_Case File Complete

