13.0 SAFETY REPORTING

[name] and [name] (PI and Consultant) will be responsible for ensuring participants' safety on a daily basis during their participation in Aim 4. Data and safety monitoring will be assured by the study's Research Team Senior key personnel: The PI and study consultants, [name] and [name], are experts in the field of dementia/chronic illness and dyadic research. Along with [name], they will make up the study's Data and Safety Monitoring Committee (DSMC). This team will act to monitor participant safety, evaluate the progress of the study, review procedures for maintaining the confidentiality of data, the quality of data collection, management, and analyses.

[name], [name], and [name] will be informed of any serious adverse events as soon as they occur and will notify the Institutional Review Board of record within 24 hours of notification. The DSMC will meet quarterly with members of the research team either in-person or by teleconference to review the study's progress, review data quality, and participants' safety. At these meetings, an evaluation of the progress of the study will be reviewed, including periodic assessments of data quality, timeliness of recruitment, the appropriateness of the strategies for recruiting participants into the study, assessing the participants' risk in using SHARE materials, and other factors that might affect the study's outcomes.

In the event of an adverse reaction, the DSMC will meet within 24 hours and the following information will be reviewed:

- Participant's study status
- How the participant was recruited into the study and the efforts that took place to retain him/her.
- The nature of the adverse reaction and a determination of how the participant's safety has been threatened as a result.
- A recommendation for how to treat the adverse reaction. In most cases, a recommendation would be to discontinue the individual's participation in the intervention and/or to withdraw the participant from the study. In more severe cases, the participant might be referred to an identified expert (the Alzheimer's Association, a geriatric care manager or licensed clinical social worker, etc.).
- If the adverse reaction is deemed to be very serious (i.e., suicidal risk or the health/well-being of the participant is in jeopardy), the case will be reported to the appropriate authorities to intervene on the situation immediately.

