- Any significant adverse reactions will be reported to the IRB within 24 hours of notification.

For the purposes of this study, a participant is considered enrolled if they have successfully completed the screening procedure outlined above. This study will be monitored by the DSMC specified above.

After being enrolled in the study, participant safety will be monitored regularly by the PI with reports being sent to the DSMC quarterly, in advance of the meetings.

As this is a minimal risk psychosocial activity intervention no AEs or SAEs are expected per NIH definitions, as it is unlikely that the risks of the study will affect medical outcomes or occurrences. However, if any AEs do occur, whether they appear study-related or not, they will be reported to the DSMC and the IRB within 48 hours of occurrence. Any deaths to study participants, from whatever cause, will be reported within 24 hours. The DSMC and IRB will then make the determination of whether they should be reported to the NIA.

If any AEs or SAEs occur, the PI will, with the assistance of the DSMC, determine if any modifications need to be made to the study protocol and procedures.

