13.1 Specification of Safety Parameters

Safety parameters for the control condition will be assessed after each single session is completed, by clinical assessment. For experimental session (SHARE), safety parameters will be assessed after each session, also by clinical assessment. Criteria for concern includes adverse behavioral changes, significant change in diagnosis or prognosis, and suicidal ideation. If a participant reports changes at the start of a session, the SHARE Counselor will immediately notify the study team, and programming will either resume or stop, depending upon the nature of the report. If information is shared that falls within the identified criteria for concern at any point, the SHARE Counselor will be instructed to contact the study PI immediately for guidance. If this occurs at a clinical level that then results in an AE it will be reported to the DSMC and IRB.

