13.6 Follow-up for Adverse Events

The occurrence of an adverse event (AE) or serious adverse event (SAE) may come to the attention of study personnel during study visits and interviews of a study participant presenting for medical care, or upon review by a study monitor.

All AEs including local and systemic reactions not meeting the criteria for SAEs will be captured on the appropriate case report form (CRF). Information to be collected includes event description, time of onset, qualified medical professional's assessment of severity, relationship to study product (assessed only by those with the training and authority to make a diagnosis), and time of resolution/stabilization of the event. All AEs occurring while on study must be documented appropriately regardless of relationship. All AEs will be followed to adequate resolution.

Any medical condition that is present at the time that the participant is screened will be considered as baseline and not reported as an AE. However, if the study participant's condition deteriorates at any time during the study, it will be recorded as an AE.

Changes in the severity of an AE will be documented to allow an assessment of the duration of the event at each level of severity to be performed. AEs characterized as intermittent require documentation of onset and duration of each episode.

The PI will record all reportable events with start dates occurring any time after informed consent is obtained until 7 (for non-serious AEs) or 30 days (for SAEs) after the last day of study participation. At each study visit, the investigator will inquire about the occurrence of AE/SAEs since the last visit. Events will be followed for outcome information until resolution or stabilization.

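### A non-fatal SAE falls under two conflicting IRB deadlines, and the two relatedness codes leave an event of uncertain cause without a valid code

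*Protocol*

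**What the plan says.** **Deadlines.** Section 13.0 expects three named people to learn of these events at once: they "will be informed of any serious adverse events as soon as they occur". Their duty towards the IRB is then given its own limit, which runs from the time they are told: they "will notify the Institutional Review Board of record within 24 hours of notification". Further down, the same section adds: "Any significant adverse reactions will be reported to the IRB within 24 hours of notification". It does not define that term, whereas section 13.2 defines AE and SAE. Section 13.0 then says of AEs generally that, "whether they appear study-related or not, they will be reported to the DSMC and the IRB within 48 hours of occurrence". Section 13.3 names SAEs as well: "AEs and SAEs will be reported to the DSMC and the IRB by the PI within 48 hours of occurrence". Sections 13.0 and 13.3 both give deaths a 24-hour limit without saying when the clock starts. Section 13.2 gives a range of 24 to 48 hours for reports to the DSMC, also without a clock start.

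**How events come to light.** Section 13.6: "At each study visit, the investigator will inquire about the occurrence of AE/SAEs since the last visit". The counselors' treatment-arm data collection procedures, on the case file: "Here you will report any major changes that either care partner has experienced since the last time you spoke with/met them". Section 13.1: "If a participant reports changes at the start of a session, the SHARE Counselor will immediately notify the study team".

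**Relatedness.** Section 13.5 requires every AE to be classified with a two-level code. Related requires clear causal evidence and the exclusion of other contributing factors. Not Related requires full independence or a definite other cause and, in every case, a documented and conclusive alternative explanation.

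**The concern.** The two IRB rules cover the same event class and the same recipient. They cannot be read as a general rule with an exception, because section 13.3 names SAEs expressly and sets aside only deaths. One SAE report can therefore be on time under one section and late under the other. An occurrence-based clock also cannot be met when an event is learned of late enough.

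On relatedness, an assessor facing an event of uncertain cause must set aside one of the two definitions in order to enter a code. Section 13.2 asks the DSMC to identify problems related to the study, and it would be working with codes that do not follow their stated definitions. Section 13.5 also promises a level of detail suited to a non-drug study, yet defines Related with drug, laboratory and rechallenge terms that do not fit a counseling program.

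**Working it through.** **Deadlines on one clock.** Let L be the hours from occurrence to notification.

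- Section 13.0: 24 hours from notification, so due at L + 24 hours after occurrence.
- Section 13.3: due at 48 hours after occurrence.
- Equal when L + 24 = 48, that is, L = 24.

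| L (h) | Section 13.0 due (h) | Section 13.3 due (h) | Earlier deadline |
|---|---|---|---|
| 0 | 24 | 48 | 13.0, by 24 h |
| 12 | 36 | 48 | 13.0, by 12 h |
| 24 | 48 | 48 | equal |
| 36 | 60 | 48 | 13.3, by 12 h |
| 48 | 72 | 48 | 13.3, by 24 h; expires at the moment of notification |
| 72 | 96 | 48 | 13.3, by 48 h; expired 24 h before notification |

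Below L = 24, following section 13.3 alone can breach section 13.0. Above it, following section 13.0 alone can breach section 13.3. Above L = 48, section 13.3 cannot be met.

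**Is a large L realistic?** Let H be the hours from onset to the session at which the event is first mentioned. Section 13.1 makes the counselor's notice to the team immediate. If that notice starts the section 13.0 clock, L = H and section 13.0 falls due at H + 24, which exceeds 48 when H > 24. The 24 hours allowed for the Adverse Event Form is a separate limit and is not added to L.

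The treatment period is 8 to 10 weeks (section 8.0) with 5 to 6 sessions. Dividing weeks by sessions gives 56/6 ≈ 9 days to 70/5 = 14 days per session. The post-session call comes at most 48 + 48 = 96 hours (4 days) after a session: data are due within 48 hours and the call follows within 48 hours of their receipt. At even spacing, about 9 − 4 = 5 days or more then remain before the next contact. An event first disclosed at a session can easily be more than 48 hours old.

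**Relatedness.** Take an event with plausible timing, no clear causal proof and no conclusive other cause.

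- Related: not met, because causation is not clearly shown and other factors are not excluded.
- Not Related: not met, because no conclusive alternative can be documented.
- There is no third category and no default rule.

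The two codes therefore do not cover all events. Section 13.5 also speaks of grading the degree of certainty, which two categories that both demand near-certainty cannot do.

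**The case against.** **The deadlines can usually be met together.** Neither rule forbids early reporting, so for L up to 48 hours a report made by the earlier deadline satisfies both. On the path section 13.0 intends, L is near zero and meeting 24 hours also meets 48. This is correct, but the protocol does not tell staff to use the earlier deadline, and the approach fails once L exceeds 48.

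**The form may settle it.** Section 13.3 says the Adverse Events Reporting Form carries the required timeline. It is not among the documents and may determine what staff actually do. The protocol text would still contradict itself.

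**L = H is a reading.** No section says that a counselor's notice to the team is the notification that starts the section 13.0 clock. That is true. If the clock started only when the Adverse Event Form arrived, up to 24 hours later, L could reach H + 24 and the section 13.0 deadline H + 48, so the two rules could part for any H above zero.

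**Little depends on the relatedness code.** All events are reported and documented whatever their relationship, no by-arm comparison of related events is planned, and the DSMC analyzes the data itself. Rechallenge is requested only where needed, and the wording offers a non-pharmacological alternative. These points limit the consequence and make the drug wording partly an editorial matter. The reminder in section 13.5 to keep the study product under suspicion points away from Not Related, but it is not a coding rule and does not relax the test for Related.

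**Few events are expected.** Section 13.0 expects none. That limits the likely number of cases but does not make the rules consistent.

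**Conclusion.** Both parts hold. A non-fatal SAE has two IRB deadlines that agree only when the team learns of it exactly 24 hours after occurrence, and the section 13.3 deadline is unattainable when that delay exceeds 48 hours. The relatedness categories are not exhaustive.

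The deadline conflict follows from the text alone. Its occurrence on the session route rests on two assumptions: that the counselor's immediate notice starts the section 13.0 clock, and that sessions are roughly evenly spaced. How many SAEs would be learned of after more than 24 hours, and how many events would be of uncertain cause, cannot be estimated from the protocol. No endpoint or efficacy analysis is affected. These are stated safety rules that fail as written, and they should be corrected.

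**What to change.** - Reconcile sections 13.0, 13.1, 13.2 and 13.3, the counselors' data collection procedures and the Adverse Events Reporting Form. State one deadline and one clock start for each event class (AE, SAE, death) and each recipient (DSMC, IRB), on a clock that can be met when an event is learned of late. Which time limit applies is for the sponsor and the IRB to settle.
- Define the significant adverse reaction or replace the term with AE or SAE.
- State when the 24-hour clock for deaths starts.
- Redefine the two relatedness categories in section 13.5 so that every event has exactly one code, for example reasonable possibility versus no reasonable possibility that participation contributed. Remove the drug, laboratory and rechallenge wording.

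The cost is revised wording in the protocol and the AE form. With complementary definitions slightly more events may be coded as related; the protocol gives no basis for estimating how many.

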13.4 Severity of Event

All AEs will be assessed by a qualified medical professional. Events will be graded using the criteria below. Since this is a non-medical study, no toxicity tables or like criteria can be utilized.

For adverse events (AEs) the following guidelines will be used to describe severity.

Mild – Events require minimal or no treatment and do not interfere with the participant's daily activities.

Moderate – Events result in a low level of inconvenience or concern with the therapeutic measures. Moderate events may cause some interference with functioning.

Severe – Events interrupt a participant's usual daily activity and may require systemic drug therapy or other treatment. Severe events are usually potentially life-threatening or incapacitating. Of note, the term "severe" does not necessarily equate to "serious."

13.5 Relationship To Study Intervention

All AEs will have their relationship to study participation assessed with a level of specificity appropriate to the non-pharmacological study design. This study will use a binary assessment (related/not related) for determining AEs. Evaluation of relatedness will consider etiologies such as natural history of the underlying disease, concurrent illness, concomitant therapy, study-related procedures, accidents, and other external factors.

All adverse events (AEs) must have their relationship to study intervention assessed by a qualified medical professional who examines and evaluates the participant based on temporal relationship and his/her clinical judgment. The degree of certainty about causality will be graded using the categories below. In a clinical trial, the study product must always be suspect.

Related – There is clear evidence to suggest a causal relationship, and other possible contributing factors can be ruled out. The clinical event, including an abnormal laboratory test result, occurs in a plausible time relationship to

study intervention administration and cannot be explained by concurrent disease or other drugs or chemicals. The response to withdrawal of the study intervention (rechallenge) should be clinically plausible. The event must be pharmacologically or phenomenologically definitive, with use of a satisfactory rechallenge procedure if necessary.

Not Related – The AE is completely independent of study intervention administration, and/or evidence exists that the event is definitely related to another etiology. There must be an alternative, definitive etiology documented by a qualified medical professional.]

13.6 Follow-up for Adverse Events

The occurrence of an adverse event (AE) or serious adverse event (SAE) may come to the attention of study personnel during study visits and interviews of a study participant presenting for medical care, or upon review by a study monitor.

All AEs including local and systemic reactions not meeting the criteria for SAEs will be captured on the appropriate case report form (CRF). Information to be collected includes event description, time of onset, qualified medical professional's assessment of severity, relationship to study product (assessed only by those with the training and authority to make a diagnosis), and time of resolution/stabilization of the event. All AEs occurring while on study must be documented appropriately regardless of relationship. All AEs will be followed to adequate resolution.

Any medical condition that is present at the time that the participant is screened will be considered as baseline and not reported as an AE. However, if the study participant's condition deteriorates at any time during the study, it will be recorded as an AE.

Changes in the severity of an AE will be documented to allow an assessment of the duration of the event at each level of severity to be performed. AEs characterized as intermittent require documentation of onset and duration of each episode.

The PI will record all reportable events with start dates occurring any time after informed consent is obtained until 7 (for non-serious AEs) or 30 days (for SAEs) after the last day of study participation. At each study visit, the investigator will inquire about the occurrence of AE/SAEs since the last visit. Events will be followed for outcome information until resolution or stabilization.

13.7 Unanticipated Problems

Upon notification of an Unanticipated Problem, the Experimental Team Leader will notify all appropriate parties as described in the protocol:

The Experimental Team Leader will immediately notify the Principal Investigator.

The PI will send a notification email to the IRB.

The PI will advise the Study Team regarding screening, enrollment, and ongoing participation. Upon advisement by the IRB, the Principal Investigator will determine the study's status and notify the Study Team.

